Current standard imaging of early recurrent prostate cancer is insufficient. Accurate detection of tumor locations is essential as the clinical management varies from active surveillance to targeted local to systemic therapy⁷. Per NCCN guidelines at the time of biochemical recurrence, imaging is performed to detect and characterize the disease to determine treatment or guide change in management. Imaging can evaluate anatomic or functional parameters and the following imaging is recommended as standard techniques at this time-point:

- Imaging is performed for the detection and characterization of disease to select treatment or guide change in management.
- Anatomic imaging techniques include plain film radiographs, ultrasound, CT, and MRI.
- Functional imaging techniques include radionuclide bone scan, PET, and advanced MRI techniques such as spectroscopy and diffusion-weighted imaging (DWI).

More specifically, Current U.S. guidelines recommend either a radionuclide bone scan, abdominopelvic CT, multi-parameter MRI or – where available - choline PET/CT for patients with rising PSA or clinical symptoms⁷. The probability of a positive bone scan is reported to be <5% with a serum PSA level of <7 ng/mL. A CT scan will only be positive in 11–14% of patients

with BCR⁸. Additionally, in a study with 132 patients, the mean PSA level of patients with a positive CT scan was 27.4 ng/ml⁸.

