^{68}Ga -PSMA-11 PET positive findings will be validated as true or false positive as outlined in more detail below. False negative ^{68}Ga -PSMA-11 PET findings may be determined based on biopsies obtained from lesion identified on conventional imaging that are negative on ^{68}Ga -PSMA-11.

Rationale for applied response criteria:

RECIST 1.1 defines a size decrease of at least 30% as response (either partial or complete), while an increase of at least 20% is considered progressive disease ^{42,43}. The decline of serum PSA of 50% or more is a commonly used criterion for treatment response following systemic treatment of metastatic prostate cancer ⁴⁴⁻⁴⁶.

Following the ^{68}Ga -PSMA-11 PET/CT scan, focal therapies of metastatic lesions may be performed without systemic treatment. Therefore, anatomic size variations can be suitable endpoints in absence of histological verification. In patients with solitary lesions, PSA reductions following focal treatment may indicate a true positive scan finding even in absence of significant size changes.

^{68}Ga -PSMA-11 PET validation based on follow-up imaging:

- i) Lymph nodes will be assessed by change in size. ^{68}Ga -PSMA-11 positive lymph nodes will be considered:
 - (1) True positive:
 - If on follow-up imaging within 3-12 months, lymph nodes seen on CT or MRI decrease by more than 30% (for patients undergoing systemic treatment of focal therapy at this site) or increase by more than 20% in short axis diameter (with a minimum of 3 mm in change in size).
 - If patients with solitary lymph node regions show a decrease of PSA by greater than 50% after targeted treatment (i.e. external beam radiation) and the lymph nodes do not change in size (less than 30% decrease or less than 20% increase in short axis diameter).
 - (2) False positive:

- If on follow-up imaging within 3-12 months, sites of initial ⁶⁸Ga-PSMA-11 positive lymph node lesions seen on CT or MRI decrease by more than 30% *without* systemic therapy or focal therapy at this site.

- If ⁶⁸Ga-PSMA-11 positive lymph node lesions do not meet the criteria for above false positive or true positive findings.

ii) Visceral lesions (non-lymph node soft tissue or organ) will be assessed by change in size. ⁶⁸Ga-PSMA-11 positive visceral lesions will be considered:

(1) True positive:

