- If on follow-up imaging within 3-12 months, visceral lesions seen on CT or MRI decrease by 30% (for patients undergoing systemic treatment of focal therapy at this site) or increase by 20% in largest diameter.

- If patients with solitary visceral metastasis show a decrease of PSA by greater than 50% after targeted treatment (i.e. external beam radiation) and lesions do not change in size (less than 30% decrease or 20% increase in largest diameter).

(2) False positive:

- If on follow-up imaging within 3-12 months, sites of initial ⁶⁸Ga-PSMA-11 positive lymph node lesions seen on CT or MRI decrease by more than 30% *without* systemic therapy or focal therapy at this site.

- If ⁶⁸Ga-PSMA-11 positive lymph node lesions do not meet the criteria for above false positive or true positive findings.

iii) ⁶⁸Ga-PSMA-11 positive bone lesions will be considered:

(1) True positive:

- If there was a corresponding positive sclerotic lesion on the CT portion of the ⁶⁸Ga-PSMA-11 PET.

- If there is focal uptake seen on the baseline bone scan performed within one month of ⁶⁸Ga-PSMA-11 PET.

- If there is a lesion noted on the initial MRI performed within one month of ⁶⁸Ga-PSMA-11 PET.

- If within 12 months follow-up CT demonstrates development of sclerosis.

- If within 12 months follow-up MRI demonstrates a new bone lesion.

- If within 12 months follow-up bone scan demonstrates new focal uptake.

(2) False positive:

- If ⁶⁸Ga-PSMA-11 positive bone lesions do not meet the criteria for true positive findings.

iv) ⁶⁸Ga-PSMA-11 positive prostate bed and prostate lesions will be considered:

(1) True positive:

- If on follow-up imaging within 12 months, lesions seen on CT or MRI decrease by 30% (for patients undergoing systemic treatment of focal therapy at this site) or increase by 20% in largest diameter.
- If patients with prostate bed lesions show a decrease of PSA by greater than 50% after targeted treatment (i.e. external beam radiation) and lesions do not change in size (less than 30% decrease or 20% increase in largest diameter).

(2) False positive:

- If on follow-up imaging within 3-12 months, sites of initial ⁶⁸Ga-PSMA-11 positive lymph node lesions seen on CT or MRI decrease by more than 30% *without* systemic therapy or focal therapy at this site.
- If ⁶⁸Ga-PSMA-11 positive lymph node lesions do not meet the criteria for above false positive or true positive findings.

c) Histopathology/Biopsy:

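### The PSA-fall route to true positive does not say how a focally treated lesion with no measurable CT/MRI correlate is scored; read literally, such a lymph node becomes a false positive

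*Combined protocol and SAP*

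**What the plan says.** Section 8.3.4 b) of the combined protocol and SAP classifies PET-positive lesions from follow-up. Nodes, visceral lesions and prostate or prostate-bed lesions each have two routes to true positive.

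- **Size route.** For nodes it applies where "lymph nodes seen on CT or MRI decrease by more than 30" percent under treatment, or grow by more than 20%, subject to "with a minimum of 3 mm in change in size". The visceral and prostate-bed bullets are likewise limited to lesions visible on CT or MRI.
- **PSA route.** For nodes: "If patients with solitary lymph node regions show a decrease of PSA by greater than 50% after targeted treatment", "and the lymph nodes do not change in size (less than 30% decrease or less than 20% increase in short axis diameter". For visceral and prostate-bed lesions the second condition is "and lesions do not change in size (less than 30% decrease or 20% increase in largest diameter".

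The rationale earlier in the same section gives the purpose of the PSA route: in patients with solitary lesions, "PSA reductions following focal treatment may indicate a true positive scan finding even in absence of significant size changes".

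The node rule ends with a catch-all. A lesion is a false positive if PET-positive "lymph node lesions do not meet the criteria for above false positive or true positive findings". The same sentence, still naming lymph nodes, is printed under visceral and prostate-bed lesions. No indeterminate or unevaluable class is defined. Bone lesions have no PSA route and a catch-all of their own.

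These rules feed the per-patient and per-region PPV in 8.3.5 item 1, which combines histopathology with conventional-imaging follow-up (the composite PPV here). Under 8.3.1 the primary PPV uses patients with histopathology.

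**The concern.** The two parts of the PSA route are joined by a conjunction, and the second part is expressed as a percentage of a diameter. A lesion seen only on PET has no baseline diameter, so that percentage does not exist. The plan does not say whether the condition is then met, failed or not assessable.

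This matters because a PSA fall after focal treatment is the only follow-up evidence left for such a lesion once treatment has worked and nothing appears on CT or MRI. If the condition is taken as failed, a treatment response that the rationale regards as supporting the scan is counted against it.

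The gap can also produce inconsistent scoring. Follow-up imaging is read locally and the secondary endpoints are pooled across institutions (2.3.2, 8.3.3), so sites could class identical cases differently.

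**Working it through.** The plan states no expected value, sample size or numeric power for the composite PPV, so there is no figure to reproduce. The check is a walk through the rules, followed by an illustration.

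**1. Rule walk.** Take a PET-positive lesion with no CT/MRI correlate at baseline, targeted treatment, a PSA fall above 50%, nothing appearing on later CT/MRI, and no biopsy.

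| Lesion | Size route | PSA route, literal | PSA route, lenient | Class on the literal reading |
|---|---|---|---|---|
| Lymph node (solitary region) | not available | not shown | met | false positive (catch-all) |
| Visceral (solitary) | not available | not shown | met | none assigned |
| Prostate bed | not available | not shown | met | none assigned |
| Bone | not applicable | no PSA route | no PSA route | unaffected by this wording |

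The lenient reading takes a lesion invisible on both scans as one that has not changed in size. No rule in the plan chooses between the readings. A treated patient with no later CT/MRI is not clearly covered by either.

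**2. How many patients rest on these rules.** Section 8.2.1 reports biopsies of PET-positive lesions in 13 of 316 evaluable subjects: 13/316 = 4.1%. Most of the composite PPV therefore depends on follow-up classification. The documents do not say how many of those lesions are focally treated and PET-only.

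**3. Direction and relative size.** Let P be the composite PPV if every such lesion is scored true positive. Let u be the share of those true positives that can reach that class only by the PSA route without a measurable lesion. Both are assumptions.

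- Scored false positive: P(1 − u), a loss of Pu.
- Excluded as unclassified: P(1 − u)/(1 − Pu), a loss of Pu(1 − P)/(1 − Pu).
- Scored true positive: P, no loss.

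The exclusion loss is the false-positive loss times (1 − P)/(1 − Pu), which is below 1 whenever u is below 1.

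| P | u | Scored false positive | Excluded |
|---|---|---|---|
| 0.75 | 5% | 0.713 | 0.740 |
| 0.75 | 10% | 0.675 | 0.730 |
| 0.75 | 20% | 0.600 | 0.706 |
| 0.75 | 30% | 0.525 | 0.677 |
| 0.95 | 10% | 0.855 | 0.945 |
| 0.95 | 30% | 0.665 | 0.930 |

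Example: P = 0.75, u = 10% gives 0.75 × 0.90 = 0.675, or 0.675/(1 − 0.075) = 0.730. The losses are 7.5 and 2.0 points.

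**The case against.** The strongest reply is that the text does not demand a measurement. The size bullets are limited to lesions visible on CT or MRI and the PSA bullets are not. The rationale accepts a PSA fall without significant size change, and the secondary objective in 2.2 lists clinical follow-up as a source of confirmation. A lesion with no anatomical abnormality before or after can be read as unchanged. This stands as far as it goes: the defect is an undefined case, and a reader who infers that the route always needs a measured percentage change goes beyond the text. It does not settle the matter, because the percentage gloss supports the other reading equally and the catch-all then decides the class for nodes.

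A reader might also infer that every treated PET-only lesion falls to false positive. That is literal only for nodes. Visceral and prostate-bed lesions are left without a class, and bone is not touched.

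A third tempting step starts from the statement in 1.2 that "A CT scan will only be positive in 11–14% of patients" with biochemical recurrence, concludes that 86–89% of treated PET-positive lesions lack a correlate, and multiplies by an assumed treated share to claim a large loss in PPV. The documents do not support this. The figure is the share of all recurrence patients whose CT is read as positive. It is not the share of treated PET-positive lesions without a measurable diameter; a small node may be measurable on a CT that is not called positive, and MRI also counts. The figure makes PET-only lesions plausible and no more.

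Two further points have weight. A stricter anatomical standard is defensible: the PSA bullets do not exclude concurrent systemic therapy, and the prostate-bed bullet is not limited to solitary lesions, so a looser rule could bias PPV upward. And 8.3.4 b) expects every patient to have conventional imaging within 3–12 months, so absent follow-up imaging is a general reference-standard problem. That is a reason not to let PSA alone confirm a lesion that was never re-imaged.

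**Conclusion.** The concern holds in limited form. In 8.3.4 b) i), ii) and iv) the PSA route leaves treated lesions without a measurable CT/MRI correlate undefined. On the literal reading, nodes of this kind become false positives, against the stated rationale, and visceral and prostate-bed lesions have no class.

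If these lesions are cancer, the composite PPV, per patient and per region, is biased downward, and by less where unclassified lesions are excluded than where they are scored false positive. Under the lenient reading there is no bias. The amount cannot be computed, because the documents give neither the share of such lesions nor an expected composite PPV; the tabulated values rest on assumed P and u.

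The histopathology-based primary PPV is not directly affected. The one indirect link is 8.3.4 c), which sends some negative nodal biopsies (suspicious node still present, or wrong node sampled) back to follow-up imaging. The point should be settled before the composite PPV is analysed, but it does not threaten the primary conclusion.

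**What to change.** 1. In the PSA bullets of 8.3.4 b) i), ii) and iv), state that the size condition is also met when the lesion has no measurable correlate at baseline and none appears on follow-up CT/MRI.
2. For the same three lesion types, class lesions with neither follow-up CT/MRI nor histopathology as unevaluable, not false positive.
3. In the false-positive bullets of ii) and iv), replace the lymph-node wording with the lesion type that each rule covers.
4. Report the number of lesions confirmed by PSA alone. Give composite PPV, per patient and per region, three ways: with these lesions and the unevaluable ones counted as true positive, excluded, and counted as false positive.

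The cost is a clause in three bullets, one new class, a wording correction and a short sensitivity table. Patient care and data collection do not change. The downside is that more confirmations rest on PSA alone; the sensitivity rows do not remove that risk, but they show how much the result depends on it.

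### Composite PPV: the visceral and prostate-bed false-positive rules name only lymph nodes, and lesions without follow-up have no class of their own, so the result depends on how section 8.3.4 b) is read

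*Combined protocol and SAP*

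**What the plan says.** Section 8.3.4 b) says that PET-positive findings "will be validated as true or false positive as outlined in more detail below". Under a heading on "validation based on follow-up imaging" it then gives rules for four lesion types.

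- **Nodes (i).** True positive by a size change on follow-up imaging, or by a PSA fall after targeted treatment of a solitary nodal region "and the lymph nodes do not change in size". False positive by shrinkage without treatment, or by a residual bullet for the case where "positive lymph node lesions do not meet the criteria for above false positive or true positive findings".
- **Visceral lesions (ii),** defined as non-nodal. The true-positive criteria are written for visceral lesions. Both false-positive bullets repeat the nodal text.
- **Bone (iii).** There are six true-positive routes. Three need only imaging from around the time of the PET; one begins "If there was a corresponding positive sclerotic lesion on the CT portion of the" PET. The lesion is false positive if "positive bone lesions do not meet the criteria for true positive findings".
- **Prostate bed and prostate (iv).** The item states how "positive prostate bed and prostate lesions will be considered". Its true-positive criteria fit the lesion type, but both false-positive bullets again repeat the nodal text.

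The endpoint that relies on these rules is the per-patient and per-region PPV in 8.3.5 item 1. Follow-up imaging is not a study procedure: it is expected as clinical care (8.3.4 b), follows local standard of care (5.3), and for osseous or metastatic lesions is left to the treating physician (5.3.1.2). Section 8.3.1 sends every patient without a histopathology correlate to the secondary analyses and sets no evaluability condition.

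**The concern.** Two faults pull in opposite directions.

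First, a visceral or prostate-bed lesion that fails its true-positive criteria matches no false-positive bullet as written. If such lesions dropped out of the denominator, PPV would rise.

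Second, the residual bullets for nodes and bone catch everything that meets no other criterion. On plain wording this includes an unbiopsied node that was never usefully re-imaged, and an unbiopsied bone lesion with neither follow-up nor a baseline correlate. Absence of evidence then counts as evidence of a false positive, and PPV falls as follow-up becomes less complete.

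The imaging rules will carry most of the weight. Section 8.2.1 reports biopsies of PET-positive lesions in 13 of 316 evaluable subjects at this site (4.1%). The data are to be pooled across sites for an NDA (1.1), and 8.2.1 claims adequate power for the per-region tests in the pooled 1,500. Two analysts with the same data could report different composite PPVs.

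**Working it through.** **The plan's own figure.** The documents give no expected value or numerical power for the composite PPV. The nearest figure is the 80% power for the primary PPV (50% against 75%, about 24 biopsied patients, one-sided 0.05). A normal approximation with null variance gives 0.25 × √24 / 0.5 − 1.645 = 0.804, hence 78.9%. That agrees, and it is not at issue here.

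**Can a node be true positive without follow-up imaging?** No. The size routes need a second image, and so does the PSA route, because it requires unchanged size. Bone differs, since three of its six routes need only baseline evidence.

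**Inputs.** The 75% is borrowed from the primary hypothesis in 8.2.1. The prostate-bed share of 30% is the anticipated share of biopsied disease in 8.2.1, applied here to all findings. Every other share below is assumed.

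**Upward effect of the literal wording.** Suppose 25% of findings in every region are false, and false prostate-bed findings cannot be scored.
- False findings lost: 0.30 × 0.25 = 0.075.
- Reported PPV: 0.75 / (1 − 0.075) = 81.1%.
- If all extrapelvic soft tissue (20% in 8.2.1) were visceral and also lost its false positives: 0.75 / (1 − 0.50 × 0.25) = 85.7%. This is an upper bound for these assumptions.

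**Downward effect for nodes.** Let p be the true PPV and f the share followed. Assume no biopsy, missing follow-up unrelated to disease, every followed cancer meeting a true-positive criterion, and every followed benign node scored false positive. On plain wording, reported PPV = p × f.

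| Without follow-up | p × f, with p = 0.75 | Unfollowed excluded |
|---|---|---|
| 10% | 67.5% | 75% |
| 20% | 60.0% | 75% |
| 30% | 52.5% | 75% |
| 40% | 45.0% | 75% |

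With an assumed 200 PET-positive nodes and 30% unfollowed, this is 105/200 = 52.5% (Wilson 95% interval 45.6 to 59.3%) against 105/140 = 75.0% (67.2 to 81.4%). These are per-lesion figures. They carry over to a patient or region only where there is a single PET-positive node.

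**Bone.** Assume 100 unbiopsied lesions: 50 with a baseline correlate (all cancer), half of the other 50 cancer, 60% followed, and every followed cancer meeting a criterion. The true PPV is 75%.
- Plain wording: 50 + 25 × 0.6 = 65 of 100 = 65%.
- Excluding the 50 × 0.4 = 20 unfollowed lesions without a correlate: 65/80 = 81.25%.
- Followed lesions only: (50 × 0.6 + 25 × 0.6) / 60 = 45/60 = 75%.

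For bone, then, simple exclusion overshoots, because lesions with a baseline correlate stay in as true positives.

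**The case against.** The wrong noun is evidently a copying slip, and the item headings show what was meant. The rules sit under a follow-up-imaging heading, nodes and visceral lesions are to be judged by change in size, and 8.3.5 item 1 speaks of imaging follow-up. The natural reading may therefore be that only followed lesions are classified. Section 8.3.1 covers all secondary endpoints, including surveys and safety, so it is not a PPV denominator rule. Section 8.2.1 already uses the word evaluable. Finally, counting unverified positives as false is a defensible conservative convention.

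Much of this stands. The followed-only reading is open, and on it the downward effect disappears. But no section states it, evaluable is not defined for this endpoint, and the bone rule under the same heading accepts baseline-only evidence, so the heading does not settle the matter. If the conservative convention is intended, the plan should say so.

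A reader might infer two further faults that the documents do not support.
- The prostate-bed PSA rule ("If patients with prostate bed lesions show a decrease of PSA by greater than 50% after targeted treatment") lacks the solitary condition used for nodes and visceral lesions. The rationale for that condition is introduced by focal treatment of metastatic lesions, the prostate bed is a separate region in Table 1, and the nodal rule speaks of solitary regions. The omission may be deliberate.
- Section 8.3.4 might seem to ignore clinical follow-up altogether. The PSA routes are arguably a form of it. What remains is a wording mismatch: 2.2 and 8.2.1 list clinical follow-up in the reference standard, while 2.3.2 and 8.3.5 item 1 do not.

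**Conclusion.** The point holds as a fault in the scoring rules for the secondary composite PPV and should be fixed. The wrong lesion type in ii)(2) and iv)(2) is plain on the text. The missing class for unverified lesions is equally plain; its consequence depends on which of two open readings is applied.

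The size cannot be fixed from the documents, because they give no follow-up share. Under the stated assumptions, a true 75% could read about 81% through the noun error, or 67.5 down to 45% for nodes with 10 to 40% unfollowed. Bone is affected less.

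A reader might infer that the composite PPV will be biased in a known direction, or that the primary result is compromised. Neither follows. The two effects oppose each other and rest on assumed shares. The primary PPV is confirmed by histopathology and is reached only through the imaging fallbacks in 8.3.4 c) iii)(2), such as a wrongly targeted node or indeterminate bone pathology; that effect cannot be sized. Followed cancers that stay stable may also be scored false positive, but that is a separate matter which excluding unfollowed lesions does not change.

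**What to change.** 1. In 8.3.4 b) ii)(2) and iv)(2), name visceral lesions and prostate bed/prostate lesions respectively.
2. Limit the residual false-positive bullets to lesions with follow-up imaging in the stated window. Class PET-positive lesions with neither biopsy nor usable reference evidence as not evaluable, and report their number. Give PPV twice: with these lesions excluded, and with them counted as false positive.
3. For bone, also report PPV restricted to lesions with biopsy or follow-up, for the reason shown in the bone example.
4. Minor: bring the mention of clinical follow-up in 2.2 and 8.2.1 into line with 2.3.2 and 8.3.5 item 1.

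The cost is a protocol amendment approved by PRC and IRB (9.4), agreement among the pooled sites, and a few tabulations. The precision cost is small. The interval-width ratio, excluded against counted as false positive, is about √[0.75 × 0.25 / f] / √[0.75f × (1 − 0.75f)]. For 10, 20, 30 and 40% excluded in the nodal illustration, width changes by about −3, −1, +4 and +12%. Only if the PPV itself did not change would the ratio be 1/√f, that is 5, 12, 20 and 29% wider.

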- i) Localization of lesions for histopathology/biopsy will be a classified according to the regions in table 1.
- ii) ⁶⁸Ga-PSMA-11 positive findings are aimed to be confirmed by histopathology/biopsy if clinically feasible.
- iii) Histopathological procedures and biopsies will be performed as clinically indicated and as per institutional protocol.

(1) Positive HP/Biopsy: Confirmed sites of metastatic or tumor involvement by histopathology/biopsy will be discussed with the responsible physician/surgeon.

(2) Negative Biopsy: Patients with suspected tumor recurrence on ⁶⁸Ga-PSMA-11 PET with negative histopathology/biopsy will be handled as outlined below:

(a) Lymph nodes:

- For patients undergoing nodal dissection: Patients will be rescanned with dedicated CT or MRI to determine if the suspicious ⁶⁸Ga-PSMA-11 positive node was removed.
 1. If ⁶⁸Ga-PSMA-11 positive lymph node is still present, a repeat biopsy can be pursued if clinically feasible and applicable, or follow-up using imaging as described above will be performed.
 2. If the corresponding node was removed, then this will be considered a False Positive.
- For patients undergoing needle biopsy: Images of the procedure will be reviewed to determine if the correct node was biopsied.
 1. If the correct node was biopsied, then a negative biopsy will be considered a False Positive.

2. If the incorrect node was biopsied, then follow-up imaging as described above will be performed.
- (b) Bone lesions: Given the high rate of false negative biopsies for osseous metastases in patients with prostate cancer, patients with negative bone biopsies of PSMA PET positive lesions will be further evaluated:
 - If pathology demonstrates an alternative diagnosis that is known to be PSMA positive (eg Renal Cell Carcinoma metastases, Paget's disease), then this will be considered a False Positive.
 - If pathology is indeterminate, then follow-up imaging as described above will be performed to determine if the lesion is a True Positive or False Positive.
 - Additionally, a repeat ⁶⁸Ga-PSMA-11 can also be obtained, as allowable, in addition to repeat conventional imaging (CT and/or MRI) in cases of negative biopsy to determine if the biopsy was true negative or false negative.
- (3) Although not routinely performed during standard practice, immunohistochemical staining for PSMA of tumor specimens (primary and lymph node metastases) may be performed, although not required.

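### The imaging criteria for bone do not exclude a correlate reported as benign, so a lesion that section 8.3.4 calls false positive on biopsy can be called true positive without one

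*Combined protocol and SAP*

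**What the plan says.** Section 8.3.4 b) iii) lists six alternative true-positive criteria for a PSMA-positive bone lesion.

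Three are baseline findings:
- CT: "If there was a corresponding positive sclerotic lesion on the CT portion of the" PSMA PET.
- Bone scan: "If there is focal uptake seen on the baseline bone scan performed within one month of" the PSMA PET.
- MRI: "If there is a lesion noted on the initial MRI performed within one month of" the PSMA PET.

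Three are follow-up findings:
- CT: "If within 12 months follow-up CT demonstrates development of sclerosis".
- MRI: "If within 12 months follow-up MRI demonstrates a new bone lesion".
- Bone scan: "If within 12 months follow-up bone scan demonstrates new focal uptake".

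The only imaging-based false-positive class is the remainder, where "positive bone lesions do not meet the criteria for true positive findings".

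Section 8.3.4 c), under negative biopsy of bone lesions, has a separate pathology rule. It begins "If pathology demonstrates an alternative diagnosis that is known to be PSMA positive", gives renal cell carcinoma metastases and Paget's disease as examples, and labels such a lesion a false positive. If pathology is indeterminate, the lesion goes back to the imaging rules.

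The composite of histopathology and conventional imaging is the reference standard for the secondary PPV, per patient and per region (section 8.3.5, item 1). The primary analysis is limited to patients with histopathology (section 8.3.1).

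**The concern.** The pathology rule recognises that some bone lesions take up the tracer without being prostate cancer, and counts them against the scan. The imaging rule has no counterpart. A lesion that the radiologist identifies as Paget's disease still satisfies a true-positive criterion if it is sclerotic on the PET's CT, shows focal uptake on a bone scan within the month, or is noted on an MRI within the month. No criterion lets the reported diagnosis override the finding.

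This is a stated rule that gives a wrong label, and not merely missing detail. It affects the kind of false positive that the plan itself names. The resulting PPV is pooled over 1,500 patients and meant to support an NDA.

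A lesser matter is location. Only the baseline CT criterion says that the finding must correspond to the PET lesion. The other five leave this to the reader.

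**Working it through.** **1. The six criteria side by side**

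| Criterion | Site match stated | Benign report excluded | Must be new |
|---|---|---|---|
| Baseline CT, sclerotic lesion | yes | no | no |
| Baseline bone scan, focal uptake | no | no | no |
| Baseline MRI, lesion | no | no | no |
| Follow-up CT, sclerosis | no | no | yes |
| Follow-up MRI, bone lesion | no | no | yes |
| Follow-up bone scan, focal uptake | no | no | yes |

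**2. One lesion, two routes.** Take a PSMA-positive lesion that is Paget's disease.
- Biopsied, with pathology showing Paget's disease: false positive (8.3.4 c).
- Not biopsied, with a sclerotic, bone-scan or MRI correlate at baseline: true positive (8.3.4 b iii), even if the report names Paget's disease.
- Not biopsied, with no baseline correlate and nothing new on follow-up: false positive by default.

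The labels conflict in the second case only.

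**3. Size.** The plan gives no figure for how often this happens, so there is none to reproduce. Let p be the true PPV among PET-positive bone regions and f the share of false positives that the imaging rule relabels. Both are assumed.

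Apparent PPV = p + (1 − p) × f

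- p = 0.75: f = 0.10 gives 0.75 + 0.25 × 0.10 = 77.5%; f = 0.25 gives 81.3%; f = 0.50 gives 87.5%.
- p = 0.50: the same f give 55.0%, 62.5% and 75.0%.

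**4. Dilution over all findings.** Section 8.2.1 expects bone to be 35% of biopsied disease. Assume that this share holds for all PET-positive findings and that p = 0.75 in every region. Then apparent PPV = 0.75 + 0.35 × 0.25 × f, which is 75.9%, 77.2% and 79.4% for f = 0.10, 0.25 and 0.50. This is a per-finding figure. The per-patient PPV moves less if a relabelled bone lesion occurs in a patient with another confirmed lesion.

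**5. Reach into the primary endpoint.** The one route is an indeterminate bone biopsy referred back to imaging. With about 24 biopsied PSMA-positive patients (section 8.2.1), one relabelled patient moves the primary PPV by 1/24 = 4.2 points.

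**The case against.** The best defence is that the criteria are shorthand for competent readers. The opening line of iii) concerns the PET-positive lesion, so each criterion is naturally read as a test of that lesion. The lymph-node true-positive criteria omit an explicit site match too. This largely answers the location point. A reader might infer that new uptake in a rib could confirm PET uptake in a vertebra, but that requires ignoring the opening line. What remains is a wording gap worth closing because several institutions contribute data.

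The defence is weaker on benign correlates. There are partial filters: readers grade only suspected disease, central readers are trained and have the CT, the baseline CT criterion asks for a positive lesion, and clinical notes are reviewed for metastases (section 5.3). None is written as an override of the six criteria.

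Some stronger inferences should be resisted:
- **An unbiopsied Paget lesion is always a true positive.** It is so only with a qualifying finding. The follow-up criteria require something new, so a stable lesion does not meet them.
- **About 96% of bone calls rest on imaging.** Section 8.2.1 reports biopsies of PSMA-positive lesions in 13 of 316 evaluable subjects (4.1%). The 316 are not stated to be PET-positive, let alone bone-positive, so this shows that biopsy is uncommon and no more.
- **The composite PPV is biased upward overall.** Bone lesions without a correlate default to false positive, and section 1.2 describes conventional imaging as insensitive. True metastases can therefore be counted as false positives, which pulls the other way.

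**Conclusion.** The concern holds for the labelling rule. As written, section 8.3.4 b) iii) can count as true positive a bone lesion whose correlate is reported as a specific benign or other non-prostate-cancer diagnosis, which conflicts with the plan's own pathology rule. The missing site match in five of six criteria is a secondary clarification.

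This rule's own effect is to raise the secondary composite-reference PPV for region 4, and the per-patient PPV where bone is the only positive finding. The illustrative rise is 2.5 to 12.5 points for a true bone PPV of 75%. It rests entirely on assumed relabelling shares of 10% to 50%, and the documents supply neither quantity. The direction of the net bias is unknown, and the two opposing errors cannot be assumed to cancel.

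A reader might also infer that the primary result is compromised. The documents do not support that: the primary PPV is based on histopathology and is exposed at most through indeterminate bone biopsies. The change should be made, but it does not put the main conclusion in doubt.

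**What to change.** Two edits to section 8.3.4 b) iii):

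1. Preface the true-positive criteria with: *the correlate is at the site of the PET-positive lesion and is not reported as a specific benign or other non-prostate-cancer diagnosis.*
2. Add a false-positive criterion: *the corresponding CT, MRI or bone-scan finding is reported as a specific benign or other non-prostate-cancer diagnosis (for example Paget's disease), with no later evidence of metastasis.* This brings the imaging rule into line with section 8.3.4 c).

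Apply both in the pooled central analysis, to all sites and to completed cases. A change at one site only would leave two reference standards in the pooled data.

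The cost is modest. Two items per PET-positive bone lesion (site match and reported nature) have to be abstracted. Section 5.3 already provides for collecting reports of conventional imaging from the 12 months after the PET. Reports of a bone scan or MRI done shortly before the PET are already needed to apply the existing baseline criteria. The downsides are some relabelling of completed cases, coordination with the other sites, and probably a slightly lower reported bone PPV.
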